This study is a randomized control trial with an active control group. Once participants are enrolled in the study, all baseline measures and demographic information will be recorded by the participant and their sleeping partner (*Demographics*, *DemographicsPartner*, *BaselineData*, and *BaselineDataSleepingPartner*). After the baseline measures are recorded, participants will be randomized to receive either MAD or the standard conservative therapy. The MAD arm will consist of participants given a fitted mandibular advancement device that they will wear for the length of the study. The device will be fully fitted by the maxillofacial physician who specializes in maxillofacial prosthodontics, and is an expert at the fabrication of mandibular advancement devices. The standard home therapy will include daily use of medicated nasal rinses, external nasal dilator, mouth taping, and lateral positional therapy and will function as our active control group.

For those randomized to the MAD, we will arrange a meeting with the maxillofacial physician to initiate the process of fitting the device. After the device is fully fitted, which will take 4 weeks, the participants will initiate the 4-week intervention.

For those who are randomized to the standard conservative therapy, it will begin with a medicated nasal rinse (Neti-cort – nasal saline lavage with Mometasone), which will take 4 weeks to achieve therapeutic effectiveness for improved nasal breathing. After the 4 weeks of Neti-cort therapy, the standard therapy group will begin their intervention for 4 additional weeks as well. Participants in the standard home therapy will have access to an instructional video library which will correctly demonstrate how to implement the home therapies.

The sleeping partners will receive a text message each morning from the day of enrollment until study completion. The content of the text message will be the CGI-S and the sleeping partner will respond to the text message each morning.

Participants will use the intervention nightly for a period of 4 weeks after which an end of study visit will occur. At the end of study visit, all post-intervention outcomes will be recorded.

D2 Subject Selection and Withdrawal

2.a Inclusion Criteria

Participants will be recruited based on the following inclusion criteria:

- Age ≥ 18
- Report of snoring

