Informed consent will be obtained at the start of study visit prior to any research activity. To minimize the possibility of coercion or undue influence during the consent process, patients will be given the option to read through and sign the consent with the RC or alone. We will also remind the patient prior to the consent process that their ability to receive care will not be impacted by the presence or absence of consenting to the study, and that if they do consent, they can withdraw at any time. To minimize the coercion to finish the study, the participants will be reminded that if they do not finish the study, they will still be compensated on a pro-rated basis for the previously completed steps.

All assessments will be conducted either in person or virtually via HIPAA-compliant online surveys at baseline and then throughout the study course virtually or over the telephone.

2.e Randomization Method and Blinding

Participants will be randomized according to computer-generated code to receive either the mandibular advancement device or standard at-home therapy. [name] will provide the randomization table to the co-investigator, [name].

Due to the nature of the randomization process, blinding during the data collection phase will not be possible as the primary researcher will have to coordinate a specific initial visit with either the maxillofacial physician or [name], the otolaryngology specialist. Participants cannot be blinded either as the treatment modalities differ in a way which makes adequate blinding not possible. [name] will be blinded to randomization. Prior to data analysis, [name] will blind groups as “A” and “B” so that the team will not know which intervention corresponds to A and B throughout both the data analysis and manuscript writing process.

2.f Risks and Benefits

Mandibular Advancement Device. Risks of the Prosomnus sleep and snore device include drooling, temporomandibular disturbances, tooth pain, TMJ disturbances, and movements of the teeth that can change a person’s bite. All these risks are uncommon and resolve after cessation of use. These risks will be minimized using a morning

repositioning device each morning after the Mandibular Advancement Device is worn. Benefits of the device include a reduction in snoring intensity and severity.

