Lateral positional therapy. Lateral positional therapy consists of interventions to encourage lateral sleeping (i.e., “snore” ball, hugging pillow), which reduces the anatomical obstructions of snoring.

3.b *Treatment Regimen*

3b.1 *Interventional arm*

After the device is fitted by the maxillofacial physician, the participant will take the device home and wear it during sleep for a period of four weeks.

3b.2 *Conservative treatment arm*

Participants in this group will undergo a nightly medicated nasal rinse consisting of 240 ml nasal saline lavage with 2mg Mometasone. This mometasone nasal rinse will occur for a 4-week period prior to beginning the other three conservative therapy interventions. After the 4-week period of the mometasone nasal rinse the other three

conservative therapy interventions (external nasal dilator, mouth taping, and lateral positional therapy) will begin and occur simultaneously each night as described above.

3.c Method for Assigning Participants to Intervention Groups

The participants will be assigned using permuted block randomization in a 1:1 allocation between two arms: the MAD intervention and the conservative therapy intervention.

3.d Preparation and Administration of Study Intervention

The MAD will be delivered to the participants during the initial visit with the maxillofacial physician. Participants will self-insert the device nightly during the trial.

For the conservative therapy arm, the participants will be supplied with a roll of Johnson and Johnson Band-Aid Woven Adhesive Bandages 1" x 3", one box of Breath-Right strips (either small, medium, or large), and one Neti-Pot. The participants will receive their topical glucocorticoid prescription through the mail from AdvancedRx, which is a compound pharmacy in Fort Washington Pennsylvania that specializes in nasal delivery of medications.

3.e Participant Compliance Monitoring

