There will be check-ins with the study participants every two weeks conducted through the participant's preferred communication method (i.e., phone call or video call) to answer questions and ensure participants are adhering to protocol requirements. Participants will be asked to keep a paper calendar for daily notes of side/adverse effects and study barriers. The paper calendar will be mailed back to the RA after study completion, or a photo of the paper calendar will be sent attached to an email to the RA. Treatment compliance data and rates of side effects will be collected in the two groups. Collection of compliance will occur through a nightly log of compliance, which the participants will receive via REDCap from the research team and fill out throughout the study.

3.f Prior and Concomitant Therapy

Participants will not qualify for the study if they are on any concomitant therapy for snoring not assigned by the study team. Participants who have tried prior therapy for the treatment of snoring will be eligible for the study. Information will be gathered on their use of prior or current therapies when determining study eligibility.

3.g Packaging

All packing of material will consist of the consumer packaging for all interventions except for the Mometasone. AdvancedRx will ship the participants the Mometasone via UPS or FedEx delivery directly to the participant's home.

3.h Blinding of Intervention

The Principal Investigator will conduct a pre-randomization visit with all participants in which he will explain both interventions to the participants and conduct a physical

exam. The physical exam will ensure the participants are in adequate physical health to tolerate both interventions and lack nasal polyps, temporomandibular joint disorder, and structural abnormalities. After this, the Principal Investigator will leave the visit and the other members of the study team will randomize the participants. This blinds the Principal Investigator to the intervention.

Before data analysis begins, [name] will download the data and anonymize the data into “A” and “B” groups. Only [name] will know which group belongs to which. The research team will then proceed with data analysis.

3.i Receiving, Storage, Dispensing and Return

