All conservative therapy interventions will be stored on site in the Outcomes Lab in compliance with the manufacturer recommended storage procedures. Products will be dispensed to the participants during the baseline visit if in the conservative therapy group, or at the Maxillofacial physician meeting if in the MAD group. Return of all dispensed interventions is not expected.

E Study Procedures

[figure not shown]
E1 Screening for Eligibility

Individuals who reach out with interest in the study after seeing the approved study flyer or who have contacted RA for participation in similar studies for which recruitment has ended will be asked to complete an online screening questionnaire to ensure initial inclusion criteria is met. Interested individuals are also free to directly fill out the Screening Survey in REDCap through a QR code or link before contacting the RA.

Following initial eligibility confirmation, the RA will contact the individual to schedule a baseline visit at the Center for Advanced Medicine (CAM) building in the department of Otolaryngology – Head and Neck Surgery as well as obtain a copy of the patient’s previous PSG study to ensure an AHI of < 5. At the screening/baseline visit, participants will be provided with an e-consent form through REDCap. The RA will offer each person the option to review the consent form independently or with the RA. Once the participant electronically signs the consent form, the RA will review it and sign. The REDCap software will automatically email the participant a copy of their completed form.

E2 Schedule of Measurements

Following the recruitment period and successful enrollment, baseline survey completion and randomization of participants will occur. The timeline for measurements can be seen below:

*R = Randomization

E3 Visit 1

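### The plan describes no allocation concealment, so upcoming assignments may be known to, or predictable by, the staff who enrol

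*Combined protocol and SAP*

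**What the plan says.** The allocation procedure is spread over several sections of the combined protocol and SAP.

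- **Generation and custody (2.e).** "Participants will be randomized according to computer-generated code to receive either the mandibular advancement device or standard at-home therapy". A named person "will provide the randomization table to the co-investigator". The part this co-investigator plays in screening, scheduling or consent is not stated.
- **Type (3.c).** "The participants will be assigned using permuted block randomization in a 1:1 allocation between two arms". No block size is given, nor whether it varies or is withheld from staff.
- **Execution (3.h).** After explaining both interventions and doing a physical examination, "the Principal Investigator will leave the visit and the other members of the study team will randomize the participants". The section concludes that the PI is thereby blinded.
- **Screening, consent and baseline (E1, E3).** "Following initial eligibility confirmation, the RA will contact the individual to schedule a baseline visit". The research assistant also obtains the sleep study report and handles e-consent. The research coordinator or assistant completes the baseline measures with the couple, and randomisation follows at the same visit.
- **Order (D1).** "After the baseline measures are recorded, participants will be randomized to receive either MAD or the standard conservative therapy".
- **Blinding (2.e).** "Participants cannot be blinded either as the treatment modalities differ in a way which makes adequate blinding not possible". The same section says that blinding is not possible while data are being collected.

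No section mentions sealed envelopes, a central or REDCap release of assignments, or a separation between the person holding the table and those who recruit.

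**The concern.** Randomisation protects against selection bias only if the person deciding whether and when a couple enters cannot foresee the arm. Here a list exists within the study team, unnamed team members use it on site, and assignments already made are visible because treatment is open. Nothing in the text keeps the next assignment from the research assistant or coordinator.

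There is room to act on such knowledge. Under 2.d candidates set their own pace before the first visit. Under E1 staff arrange the visit date. Some entry conditions need judgement, such as the state of the teeth (2.b) and fitness to tolerate either treatment (3.h). A couple thought likely to respond could be encouraged, delayed or discouraged according to the arm that comes next.

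The primary outcome is the partner's own global rating of improvement, given with knowledge of treatment. It is analysed per protocol (F3), and data from withdrawn participants are excluded (2.i). Selection at entry would add to these weaknesses, and a reader of the results could not tell the sources apart.

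**Working it through.** **1. The plan's own figures.** F1 gives 60 randomised, 33% dropout, 20 evaluable per group, a 30% control response and a response 20% higher with the device, read here as 20 percentage points (50%).

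- Evaluable: 60 × (1 − 0.33) = 40.2, stated as 40.
- Margin of error: 1.96 × √(0.3 × 0.7/20 + 0.5 × 0.5/20) = 1.96 × √0.023 = 0.297, stated as 30%.

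Both reproduce and neither is in dispute. The plan gives no figure on concealment.

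**2. With sight of the table.** All 60 of 60 assignments are known.

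**3. Without the table, from assignments already made.** Assume one fixed block size b = 2m, known to staff. An assignment is certain once one arm has used its m places in the block. For b = 4 there are six possible blocks. AABB and BBAA each have two certain positions, and ABAB, ABBA, BAAB and BABA have one each. That makes 2 × 2 + 4 × 1 = 8 of 24 positions, or 33.3%. Enumerating every block for each size gives shares that equal 1/(m + 1). The last column is the share guessed correctly by always naming the arm used less so far in the block, and tossing a coin when they are even.

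| Block size (assumed) | Certain | Of 60 | Guessed correctly |
|---|---|---|---|
| 2 | 50% | 30 | 75% |
| 4 | 33.3% | 20 | 70.8% |
| 6 | 25% | 15 | 68.3% |
| 8 | 20% | about 12 | 66.6% |
| 10 | 16.7% | 10 | 65.3% |

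Unpredictable allocation would give 50% correct guesses. The count for size 8 applies the per-block rate to 60, which is not a whole number of such blocks.

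**4. Could the resulting bias be seen?** As an illustration, suppose a prognostic baseline feature is present in 30% of one arm and 50% of the other (assumed values). With n per arm, the chance that a two-sided 5% comparison flags it is Φ[(0.2 − 1.96 × √(2 × 0.4 × 0.6/n)) / √((0.21 + 0.25)/n)].

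- n = 20: (0.2 − 0.304)/0.152 = −0.68, giving about 25%.
- n = 30: (0.2 − 0.248)/0.124 = −0.39, giving about 35%.

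An imbalance as large as the hypothesised treatment effect would thus usually go unflagged, even on a measured feature.

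**The case against.** A reader might infer that assignments in this trial are in fact unconcealed. The documents do not support that. They do not say that the co-investigator who receives the table recruits anyone, or shows it to those who do. A list prepared by one person and held by another who does not recruit would be compatible with concealment. Names have been removed, so the people in 2.e cannot be matched to the team in 3.h. Section 2.e also says that one named person is blinded to randomisation.

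There are real safeguards. The PI, who makes the most judgement-based eligibility assessment, leaves before randomisation. Consent and baseline measures come first. Several entry criteria, such as the sleep study result and weight change, are fairly objective. The block calculation needs a fixed size that staff know, and 3.c does not exclude varying sizes. F3 describes baseline characteristics by group and explores confounders, so a measured imbalance could be seen and partly adjusted for.

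Most of this stands and limits the conclusion, but it does not remove it. The removed names hide who people are, whereas what is absent is a procedure. The PI's departure does not cover the research assistant or coordinator, who may be among those randomising. Completing baseline before randomisation does not help if the next arm is already known when the visit is arranged. Adjustment in 40 evaluable cases is weak and cannot reach unmeasured features.

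**Conclusion.** The point holds as a gap in the plan. A stated custody arrangement and on-site randomisation by the team come with no described mechanism that hides the next assignment from enrolling staff, who may therefore know or predict it. It does not hold as a finding that concealment failed.

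The exposure is all 60 assignments for anyone with sight of the table. For staff without it, 10 to 30 of 60 are certain, on the assumption of a fixed block size between 2 and 10 that staff know. If block sizes vary and are withheld, the exposure is smaller. The effect on the responder difference cannot be calculated from the documents, because it depends on whether anyone acts on the knowledge. A reader might also infer that such bias would be wholly undetectable. Given the descriptive and adjusted analyses in F3, the supportable statement is that it could hardly be detected or adjusted for at 20 to 30 per arm. Concealment would not cure the separate problem of an unblinded outcome rating.

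**What to change.** In 2.e, replace the hand-over of the table: the person who generates it uploads it to a locked allocation function in REDCap, which the trial already uses for e-consent and surveys. This assumes that the site's installation offers that function. If it does not, state at least that the table holder takes no part in screening, scheduling or consent.

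In 2.e and 3.h, state which role triggers randomisation, and that each assignment is released singly and only after the eligibility, consent and baseline forms have been saved. In 3.c, specify randomly varying block sizes that are not disclosed to enrolling staff.

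The cost is a small set-up effort and possibly a slight imbalance in final arm sizes. The 60 randomised, the 40 evaluable, the margin of error of about 30% and the analysis all stay as they are.

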- Prior polysomnogram (PSG) within the past 60 months showing AHI < 5 and no more than 10% gain in body weight since the prior polysomnogram
- Possess a sleeping partner who sleeps in the same room as the participant for ≥ 4 nights a week and who can report outcomes
- Access to the internet
- Ability to follow up within 1 month after adequate fitting of MAD or 4 weeks of Mometasone

Inclusion criteria for the sleeping partner:

- Age ≥ 18
- Possess a sleeping partner who sleeps in the same room as the participant for ≥ 4 nights a week and who can report outcomes
- Access to the internet

2.b Exclusion Criteria

Individuals will not be allowed to participate in this study if they meet one or more of the exclusion criteria:

- Significant hypoxemia as defined as SaO₂ below 89% for $\geq 12\%$ of the total nocturnal monitoring time
- Inability to wear a MAD defined as missing more than 50% of their dentition or their dentition is not in good condition.
- Prior intolerance of MAD
- Current treatment for OSA
- Concurrent use of sedatives or > 2 alcoholic drinks per night
- Chronic nasal obstruction due to structural anatomic defects, nasal polyps, or history of unresponsiveness to nasal rinses.

Sleeping partners do not have any exclusion criteria defined for this study.

2.c Ethical Considerations

This study relies on participation of human subjects. Informed consent will be obtained in person for each participant at the baseline visit to ensure their safety, minimize risk, and ensure full confidentiality. All assessment will be conducted via HIPAA-compliant online surveys using REDCap. We are asking the participant to engage in an intervention; however, they are not the ones solely benefitting from it as their partner is also expected to benefit.

2.d Subject Recruitment Plans and Consent Process

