Standard At-Home Conservative Therapy: Mometasone nasal rinse, mouth taping, nasal strip, lateral positional therapy. Risk of *Mometasone* include systemic absorption of the topical glucocorticoid rinse and risk of aggravating cataract and glaucoma. Risk of the *mouth taping* and *nasal strip* include skin irritation from the adhesive. Risk of *lateral positional therapy* include shoulder and hip pain during the day after sleeping.

Benefits of both treatment interventions include a reduction or cessation of snoring, leading to an improvement of quality of life for both the participant and their sleeping partner.

The consent process informs a volunteer about the study, indicates that participation is voluntary, and that he/she has the right to stop at any time. Risks are listed in the informed consent form and described orally during the consent process.

2.g Early Withdrawal of Participants

Participants may withdraw at any point in the study. The Principal Investigator can also withdraw a participant at his discretion if he determines the participant is not using the intervention correctly, for failure to adhere to the intervention, or for undermining integrity of the study.

If a participant decides to withdraw from all components of the research study, the investigator will discontinue all the current and scheduled research activities in the study.

2.h When and How to Withdraw Participants

A participant can withdraw consent for the study at any time. Participants will be allowed to end participation in the study at any point should they desire. All participants will have an exit interview to ascertain any adverse effects and discuss the reason for ending participation. The study team will follow them for safety reasons up to 30 days after stopping use of the study intervention.

2.i Data Collection and Follow-up for Withdrawn Participants

If a participant has ended participation, the only data that will be collected are the data from the exit interview and the data collected prior to withdrawal. There will not be any other follow-up or data collected from these subjects.

Data collected up to this point will not be used in the analysis, and further data will not be collected from these participants.

D3 Study Intervention

3.a Description

3a.1 Interventional Arm

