The Mandibular Advancement Device for this study will be the ProSomnus Sleep Device. It is a sleep device intended to reduce nighttime snoring and mild to moderate Obstructive Sleep Apnea in adults by holding the lower jaw forward during sleep. This

position prevents the tongue and throat from collapsing into the airway, preventing obstruction. The amount of protrusion is determined by the device's arches or by the expansion screws within the device itself. A dentist prescribes the device at an initial visit where the amount of advancement is also determined. From there, the device can be advanced manually by the participant, either through inserting the next upper or lower arch in the series of arches, or by manually adjusting the screws in the device. This is done incrementally until the prescribed advancement is achieved. Since the device can be adjusted by the participant, only an initial visit is required for fitting.

3a.2 *Conservative treatment arm*

The conservative treatment will consist of four different interventions used simultaneously.

Mometasone nasal rinse. Mometasone is an anti-inflammatory corticosteroid used for a variety of conditions. Among respiratory tract conditions, Mometasone is used for COPD, nasal polyps, asthma, chronic sinusitis, and allergic rhinitis. A nasal sinus saline irrigation (aka “Neti-Pot”) type system will deliver the Mometasone to the participant’s sinuses. For participants randomized to the conservative treatment arm, daily use of nasal lavage with mometasone will be required. Each nasal rinse will contain 2 mg of Mometasone in a 240 ml Nasal Sinus Rinse kit. The Mometasone rinse will have minimal systemic effects, as previous studies with topical steroid rinses have shown no adverse outcomes^{26,27}.

External nasal dilatory therapy. External nasal dilatory therapy consists of a stiffened adhesive strip (a “breathe-right” strip) applied externally across the nasal alae nightly. The goal is to retract and stabilize the nasal alae, dilating the anterior nasal valve and encouraging nasal breathing.

Mouth taping. Participants will receive a package of Johnson and Johnson Band-Aid Woven Adhesive Bandages (1” x 3”) tape and instructed to apply it vertically over the upper and lower lips at the columella. This encourages the participants to breathe through their nose instead of their mouth and decrease snoring amount.

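### The plan names aggravation of cataract and glaucoma as a risk of the mometasone rinse, but no written eligibility rule or named exam item asks about the eyes before randomisation

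*Combined protocol and SAP*

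**What the plan says.** The risk is stated in D2 2.f, where the hazards of mometasone include "systemic absorption of the topical glucocorticoid rinse and risk of aggravating cataract and glaucoma". The same section adds that risks appear in the consent form and are explained orally.

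The only exclusion in 2.b that bears on the rinse is nasal: "Chronic nasal obstruction due to structural anatomic defects, nasal polyps, or history of unresponsiveness to nasal rinses". At the pre-randomisation visit in D3 3.h, the exam must establish that participants are in "adequate physical health to tolerate both interventions and lack nasal polyps, temporomandibular joint disorder, and structural abnormalities".

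Allocation (3.c) is by "permuted block randomization in a 1:1 allocation between two arms". On exposure, 3a.2 says: "For participants randomized to the conservative treatment arm, daily use of nasal lavage with mometasone will be required". Section 3b.2 describes a "nightly medicated nasal rinse consisting of 240 ml nasal saline lavage with 2mg Mometasone" for four weeks before the other three measures start, while 3a.2 also says: "The conservative treatment will consist of four different interventions used simultaneously". H2 gives eight weeks in the study.

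On the size of the hazard, 3a.2 states: "The Mometasone rinse will have minimal systemic effects, as previous studies with topical steroid rinses have shown no adverse outcomes".

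**The concern.** A risk of aggravation applies to people who already have the condition, so 2.f in effect names a group at risk. One would expect a step that identifies this group before anyone is allocated to the rinse, and a rule for what to do when someone in it is found. Neither is written in 2.a, 2.b or 3.h.

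The contrast with the other arm makes this look like an omission and not a choice. Section 2.f lists tooth and jaw-joint problems as device risks. Section 2.b then excludes poor dentition and prior device intolerance, the 3.h exam looks for jaw-joint disorder, and 2.f adds a morning repositioning device. For the rinse, the written screening is nasal only, and no reason is given for admitting people with glaucoma or cataract.

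What is at stake is participant safety. Whether someone with a known eye condition is identified before exposure depends on that person mentioning it, or on the investigator thinking to ask.

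**Working it through.** The plan gives no figure on this point, so there is none to reproduce. Its sample-size figures in F1 do not enter.

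**1. Count of the written rules**

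| Place | Items | Concerning the eyes |
|---|---|---|
| 2.a participant inclusion: age, snoring, sleep study, partner, internet, follow-up | 6 | 0 |
| 2.b exclusion: hypoxemia, dentition, prior device intolerance, sleep apnea treatment, sedatives or alcohol, nasal obstruction | 6 | 0 |
| 3.h named exam conditions: nasal polyps, jaw-joint disorder, structural abnormalities | 3 | 0 |

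**2. Chance of allocation to the rinse.** With 1:1 allocation (3.c) and 30 snorers per arm (2.d), 30 / 60 = 0.5.

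**3. Exposure.** The dose is 2 mg once daily (3a.2, 3b.2).

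- Rinse in the lead-in only, one reading of 3b.2: 4 × 7 = 28 rinses, and 28 × 2 mg = 56 mg.
- Rinse throughout: 8 × 7 = 56 rinses, and 56 × 2 mg = 112 mg. This reading is supported by D1, which lists the rinse as a daily part of the home therapy, and by the statement in 3a.2 that all four measures are used together.

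These are amounts placed in the rinse. The absorbed dose is not given.

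**4. When each safeguard acts**

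- Before randomisation: consent disclosure (2.d, 2.f), the screening questionnaire (E1) and the 3.h visit. The Principal Investigator leaves after the 3.h exam and is blinded from then on.
- After randomisation: the specialist visit mentioned in 2.e, whose timing relative to the first rinse is not stated, and supply by mail on prescription (3.d).
- After exposure: two-weekly check-ins and the side-effect calendar (3.e), and removal for serious adverse effects (E7 7.a).

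**5. How many people might be involved.** The documents give neither a prevalence nor a rate of aggravation. As an assumption only, let p be the share of candidates with known glaucoma or unoperated cataract. The expected number in the 30-person rinse arm is 30p, and the number per 60 candidates needing a documented decision is 60p.

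| Assumed p | 30p | 60p |
|---|---|---|
| 1% | 0.3 | 0.6 |
| 3% | 0.9 | 1.8 |
| 5% | 1.5 | 3.0 |
| 10% | 3.0 | 6.0 |
| 20% | 6.0 | 12.0 |

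The table counts people enrolled or asked. It does not measure harm.

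**The case against.** The strongest reply is that the plan already protects this group. Section 2.f names the eye conditions and says risks are disclosed in writing and orally. Under 2.d, consent comes before any research activity. People who know they have glaucoma or a cataract are well placed to act on a named warning. In 3.h the Principal Investigator explains both arms in person and must judge the candidate fit for either, with the eye risk written in the same protocol. The steroid also needs a prescription.

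Most of this stands. A reader might infer that the plan leaves such people with no protection, or with nothing directed at the eyes. The documents do not support that: read as a whole, 2.f puts the named eye risk into the consent discussion, and 3.h allows the investigator to decline the person. What remains is narrower. Disclosure leaves the participant to connect the warning with their own history, and the 3.h clause neither prompts an eye-history question nor says how to act on the answer.

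A second reply is that the Screening Survey, the Baseline Data form and the mometasone instructions are listed attachments that are not shown, and any of them may ask or warn about this. That also stands. E1 gives the survey's purpose as checking inclusion criteria, none of which is ocular. But 3.f shows that eligibility screening also gathers therapy history, so the absence of an eye question cannot be inferred. Such a question would still lack a rule in 2.b.

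A third reply is that no harm has been shown. That is correct. A reader might infer that the rinse is unsafe for the eyes at this dose. The documents give no rate, 3a.2 states that systemic effects are minimal, and the studies cited for that statement cannot be examined here, so it is not disputed.

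**Conclusion.** The point holds as a gap between a named risk and the written eligibility rules. A person with known glaucoma or an unoperated cataract satisfies 2.a and 2.b as written, no named item in 3.h would single that person out, and the chance of being required to use the rinse daily is 1 in 2. Exposure is 28 to 56 rinses, depending on how 3a.2 and 3b.2 are reconciled.

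The size is modest. The hazard is unquantified and probably small, given the short exposure and the plan's own statement on systemic effects. The number of people affected rests entirely on an assumed prevalence. The conclusion is limited to 2.a, 2.b and 3.h and makes no claim about the forms that are not shown. Sample size and analysis are unaffected. This is a minor safety improvement.

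**What to change.** At the 3.h pre-randomisation visit, ask every candidate about current glaucoma or unoperated cataract and record the answer. Add one line to 2.b:

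*Known glaucoma or unoperated cataract, unless the investigator documents before randomisation (consulting the eye-care provider where needed) that daily 2 mg mometasone rinse for up to 8 weeks is acceptable.*

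Apply the rule to all candidates, whichever arm they would later receive. Both arms are then drawn from the same population, and an eye condition discovered later does not cause withdrawals from the rinse arm alone, which matters because 2.i drops withdrawn participants' data. The wording leaves out cataracts already removed, and it does not make outside clearance mandatory. If an existing form already asks the question, only the 2.b line is needed.

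The cost is a short amendment and one question at an existing visit. Some otherwise eligible snorers will be delayed or screened out. If 1% to 5% of candidates are affected, about 0.6 to 3 of every 60 would need a documented decision, and more if the share is higher. Not all of them would be excluded.
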